
A2 Primary Hypothesis

Hypothesis 1: Patients in the intervention arm will have significantly fewer med errors and adverse drug events, as compared to the usual care arm, at the end of the 12-month study

Hypothesis 2: The intervention arm will have significantly fewer healthcare encounters (clinic visits, ED visits and hospitalizations), leading to reduced costs, as compared to the usual care arm, at the end of the 12-month study

A3 Purpose of the Study Protocol

Due to the complexities and toxicities associated with their immunosuppressive medication regimens, kidney transplant recipients are at high-risk of developing medication safety issues which can lead to hospitalization, increased healthcare expenditures and ultimately, graft loss. Founded on preliminary information, the use of pharmacists and mHealth technology provide a promising and innovative approach to

[figure not shown]
improve medication safety in high-risk patients. The ultimate goal of this research is to demonstrate how patients, pharmacists and technology can work hand-in-hand to optimize medication-related outcomes and reduce healthcare expenditures.

B Background

B1 Prior Literature and Studies

Within kidney transplantation, despite dramatic improvements in acute rejection rates, long-term graft survival has not improved to nearly the same degree. Since 2003, there has been a 50% reduction in acute rejection rates; yet, during this same time period, the kidney allograft half-life has only increased by a modest 0.6 years.(3, 4) The most recent report from the Scientific Registry of Transplant Recipients (SRTR) demonstrates a historically low one-year acute rejection rate of <10%, with a suboptimal five-year graft survival rate of 70%.(1) Medication safety issues, which encompass both medication errors and adverse drug events, are a predominant cause of deleterious clinical outcomes in kidney transplant recipients; most notably, graft loss.

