Home-based monitoring of blood pressures and glucoses, using the FORACare system, will also transfer into the application and the report dashboard.(42, 43) The app will also give providers the ability to create and send surveys to the patient. The survey will populate on the patients' home screen as an alert message. The alert message will not disappear until the survey has been filled out and submitted. Survey responses get recorded in the app and are incorporated into the report dashboard. As part of this study, patients in the intervention cohort will receive medication side effect surveys during gaps in transplant clinic visits. The survey was developed using the validated Memphis Medication Side Effect Survey, coupled with our formative research demonstrating which side effects are associated with the adverse drug events that are most commonly associated with hospital readmission.(44-46) Patients will complete this survey and this data will then flow into the report dashboard for review as aggregate and trend information. Thus, this mHealth system will allow both the patient and transplant pharmacist to track signs and symptoms of medication safety issues.

3.b Method for Assigning Subjects to Treatment Groups

Whether a patient is in the intervention group or the control will be by random selection using a random number generator in simple blocks of 8.

3.c Subject Compliance Monitoring

Monitoring for compliance with medications, clinic visits, blood pressure and glucose monitoring (if applicable) is a part of the intervention in the intervention cohort. If subjects are not complying with data monitoring in the intervention cohort, they will be contacted by the study pharmacist to encourage use of the smartphone and any relevant Bluetooth-enabled devices. If this does not resolve the noncompliance, the subject will be contacted by the study PI to discuss continued involvement in the study. These data will not be monitored real-time in the usual care cohort. Compliance with study data capture will be monitored by the study coordinators, who are completely independent of the pharmacists providing the interventions. They will gather data via direct subject interview and through review of the subject's electronic medical records.

3.d Blinding of Study Intervention

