6. Graft failure will be defined as return to chronic dialysis, transplant nephrectomy, retransplantation or death. The study coordinator capturing clinical event data, different from the coordinator capturing medication error and adverse drug event data (to ensure independence is maintained), will review the medical record at regular intervals to determine if a study patient has developed graft failure. The timing and cause of each graft loss will be recorded for comparative analysis. Patient death will also be captured in a similar fashion, with timing and cause recorded as well.

7. Healthcare encounters will be defined as any direct encounter (face-to-face) between the study patient and a physician or advance practice provider (APP) occurring within a licensed healthcare facility and occurring during the 12-month study. These encounters will be categorized as ambulatory clinic visits, ambulatory procedure visits, acute care/emergency room visits and hospitalizations. Hospitalizations will be defined as an admission to a hospital with at least one overnight stay. Length of stay within the hospital for readmissions will also be captured. Healthcare encounters will be captured through direct study subject interviews with patients at bimonthly intervals.(36) The study coordinator will record all healthcare encounters that have occurred. If the patient has a health care encounter outside of the study institution, the research coordinator will document the type of encounter to estimate costs, as detailed below.

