8. Costs associated with care will be assessed based on data from hospital accounting at the study institution, once the study is completed. Costs will be measured from the time of randomization up until the end of the 12-month follow-up period. Analyses will include all costs associated with inpatient and outpatient care, including hospitalizations, ambulatory care visits, ambulatory procedure visits, acute care/emergency room visits and laboratory assessments. Costs uniquely associated with the intervention group will include the costs of the devices and data plan provided to the patients, time necessary for training patients on use of the technology and research pharmacist time associated with the intervention. Total costs will be calculated for each cohort. These data will be electronically captured by providing a list of patient's MRNs to hospital accounting after the completion of the study to allow for accurate and complete billing information to accrue. Costs associated with healthcare encounters that occur outside the study institution will be estimated by acquiring information from the patient regarding the type of encounter and using this data to estimate cost based on cost/charge ratios from the study institution. This will be a costs - consequences analysis (CCA) using cost effectiveness methodology, taken from the societal perspective.

F Statistical Plan

F1 Sample Size Determination and Power

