Based on previous studies conducted by our research collaborative, we estimate that approximately 64% of kidney transplant recipients in the control group will experience a medication error during the one year study (defined using the Overhage criteria).(1, 2) Our previous research demonstrates that pharmacist-led initiatives can reduce these medication errors by approximately 50%.(3, 4) Using these estimates, enrolling 104 participants (52 in each cohort), will provide 92% power in detecting a statistically significant difference in medication error event rates, with a two-tailed $\alpha=0.05$. We will also have 94% power (two-tailed, $\alpha=0.05$) to detect a 33% reduction in significant adverse drug events (CTCAE grade 3 or higher), given an estimated incidence rate of 87% in the control cohort and the strong association between medication errors and adverse drug events.(2, 5) From previous analyses, we expect that the control cohort will have a mean of 18.4 ± 2.6 healthcare encounters (clinic visits, acute care/ER visits and hospitalizations), during the one year study. We estimate the intervention group will see an 8% absolute reduction in total encounters, to a mean 17.0 encounters, with an estimated 33% relative reduction in the mean number of hospital readmissions (1.2 vs. 0.8, respectively).(2) Given these estimates (two-tailed, $\alpha=0.05$), enrolling 52 patients in each arm will provide 80% power to detect a statistically significant difference. It is estimated that the intervention will also produce a mean cost savings of at least \$2,489 per patient (\$7,658 in the control cohort and \$5,169 in the intervention cohort, with σ estimated at \$4,530).(2) This study is expected to have >80% power to detect a statistically significant difference in total post-transplant costs between cohorts, given these estimates.

For the exploratory outcomes of acute rejection, infections, graft function, graft loss and death, this study is not powered to detect statistically significant differences in these clinical events between groups. However, we expect to demonstrate meaningful clinical signals, particularly with a reduction in acute rejection. Our previous study demonstrated an acute rejection rate that was 1.8 times higher in patients experiencing a significant medication error (13.7% vs. 7.7%, respectively).(2) Thus, we expect an overall acute rejection rate of 12% in the control cohort and 9% in the intervention cohort,

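### E4 item 7 names only two-monthly patient interviews as the source of the encounter count, although study-institution accounting data on the same encounters are already to be extracted for costs

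*Combined protocol and SAP*

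**What the plan says.** Section A2 sets the hypothesis: "Hypothesis 2: The intervention arm will have significantly fewer healthcare encounters (clinic visits, ED visits and hospitalizations), leading to reduced costs". Section C2 lists resource use as a secondary aim. F1 plans for "a mean of 18.4 ± 2.6 healthcare encounters (clinic visits, acute care/ER visits and hospitalizations" in the control arm, an "8% absolute reduction in total encounters, to a mean 17.0 encounters" in the intervention arm, and states that "enrolling 52 patients in each arm will provide 80% power to detect a statistically significant difference".

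E4 item 7 defines an encounter as face-to-face contact with a physician or advanced practice provider in any licensed facility. Its capture rule is a single source: "Healthcare encounters will be captured through direct study subject interviews with patients at bimonthly intervals". The E2 schedule agrees: encounters appear as visit or tele assessments, while rejection, infection and graft outcomes appear as chart review.

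The neighbouring items differ. E4 item 2 (medication errors and adverse drug events) pairs the interview with medical-record review. Items 3, 4 and 6 (rejection, infection, graft failure) rely on record review.

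E4 item 8 obtains study-institution costs for hospitalizations, clinic visits, procedure visits and emergency visits from randomization to month 12, by sending patients' "MRNs to hospital accounting after the completion of the study to allow for accurate and complete billing information to accrue". It does not say that this extract will count or check encounters. For care elsewhere, the patient is the only stated source.

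Two other sections mention records. D3 3.c says of the coordinators: "They will gather data via direct subject interview and through review of the" electronic record. E3 3.e screens charts for new hospitalizations, for serious adverse events. Neither assigns record review to the encounter count.

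**The concern.** The planned effect is small against the total, 1.4 of 18.4 encounters, and many of these are probably routine clinic visits, which are easy to forget over two months. Forgetting at the same rate in both arms does not cancel out. It scales the difference down and adds random variation to each patient's count.

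Forgetting at different rates biases the comparison. Participants know their assignment (D2 2.e), and under D3 3.a the pharmacist follows up intervention patients at each admission or discharge. A blinded interviewer cannot correct what the patient remembers.

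Hypothesis 2 also links fewer encounters to lower costs. As written, the counts come from interviews and the in-house costs from accounting, so the two halves could disagree for the same patient with no stated rule for resolving it.

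**Working it through.** **Inputs from F1.** Control mean 18.4, intervention mean 17.0, SD 2.6 (applied to both arms), two-sided α = 0.05, 52 per arm. Randomized 68 per arm with 85% retention: 68 × 0.85 = 57.8, about 58 per arm.

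**Step 1: reproduce the plan's figure.** Difference 18.4 − 17.0 = 1.4. Noncentrality = 1.4 / (2.6 × √(2/52)) = 2.75. Power is 77.6% by noncentral t and 78.4% by the normal approximation. A reduction of exactly 8% (0.08 × 18.4 = 1.472) gives 81.6% and 82.3%. The stated 80% is therefore reproduced to rounding, with no visible allowance for missed encounters.

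**Step 2: equal recall in both arms.** Assume each encounter is reported independently with probability r. Then:

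- observed difference = 1.4r
- observed variance in an arm with mean μ = r² × 2.6² + r(1 − r)μ

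Averaged over the arms, μ = (18.4 + 17.0)/2 = 17.7. For r = 0.90: difference 1.26; variance 0.81 × 6.76 + 0.09 × 17.7 = 5.48 + 1.59 = 7.07; SD 2.66; noncentrality 1.26 / (2.66 × √(2/52)) = 2.42.

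| Assumed recall r | Observed difference | Observed SD | Power, 52 per arm | Power, about 58 per arm |
|---|---|---|---|---|
| 1.00 | 1.40 | 2.60 | 77.6% | 82% |
| 0.95 | 1.33 | 2.63 | 72.2% | 77% |
| 0.90 | 1.26 | 2.66 | 66.8% | 72% |
| 0.85 | 1.19 | 2.67 | 61.4% | 66% |

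Powers are by noncentral t. Every r below 1 is an assumption.

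**Step 3: unequal recall.** Observed difference = r(control) × 18.4 − r(intervention) × 17.0.

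- Control 93%, intervention 95% (assumed): 17.112 − 16.150 = 0.96. Power at 52 per arm is about 45%.
- The reverse, control 95% and intervention 93%: 17.480 − 15.810 = 1.67, larger than the true 1.4.
- With no true effect, a 2-point gap produces 0.02 × 18.4 = 0.37 encounters, 26% of the planned 1.4. Its sign depends on which arm recalls better.

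The mechanism the plan suggests, pharmacist contact at care transitions, points to better recall in the intervention arm. That is the first case: the benefit is understated.

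**Step 4: what records can recover.** Records at the study institution miss outside encounters. Under the same model, using records alone when 5% or 10% of encounters occur elsewhere (assumed) costs exactly as much power as recall of 95% or 90%. Records therefore cannot replace the interview, and Step 2 is an upper limit on the gain, because it applies the loss to all encounters.

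**Step 5: whether chart review elsewhere closes the gap.** The E3 3.e screening covers hospitalizations. F1 expects a mean of 1.2 readmissions among 18.4 encounters, 1.2/18.4 = 6.5%. The statement in D3 3.c is general and sits under compliance monitoring.

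**The case against.** The strongest reply is that the plan need not mean recall alone. D3 3.c describes interview plus record review, E3 3.e screens charts for hospitalizations, and item 7 has the coordinator record every encounter that has occurred. Coordinators may well check the record in practice. This stands in part: the sections need reconciling, and a recall-only design is not proven. But the rule written for this outcome, and the schedule, name only the interview, while other items name records explicitly.

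A reader might infer that patients who miss interviews are dropped. The documents do not support that. F3 analyses all randomized participants, F3 and F5 plan multiple imputation with a sensitivity analysis for data missing not at random, and D2 2.i continues outcome collection for those who stop only the intervention. A later interview might also cover a missed one, although no look-back rule is given. What remains is that counts held by the institution would be imputed.

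A reader might also infer that complete records exist and could replace the interview. They are complete at most for one institution, while item 7 counts encounters in any licensed facility.

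The power figures are open to fair challenge. No recall rate is given, the model allows forgetting but not over-reporting, and if the earlier analyses behind 18.4 ± 2.6 used similarly incomplete counts, the planning figures may already contain some of the loss. Nor does the pharmacist-contact argument show a false benefit; it points the other way. All of this stands, so the figures are illustrations.

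Finally, the primary outcome in E4, medication errors and adverse drug events, is unaffected.

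**Conclusion.** The point holds as a cheap improvement to a Hypothesis 2 outcome that is a secondary aim. The capture rule for encounters names a weaker source than one the trial already plans to obtain for most of the same encounter definition at the study institution, and the sections that mention record review do not assign it to this count.

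The direction of the power loss under incomplete recall does not depend on the rate chosen. Its size does: under assumed equal recall of 95% to 85%, about 5 to 16 percentage points, both at 52 per arm (77.6% to between 72.2% and 61.4%) and at about 58 per arm (82% to between 77% and 66%). Only the in-house part of this is recoverable. Unequal recall could matter more, but the documents do not establish that it would occur; the likelier direction is an understated benefit. The documents support neither exclusion of patients nor a spurious benefit.

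**What to change.** Amend E4 item 7 and the E2 schedule as follows.

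- Count study-institution encounters from the EHR or accounting extract for every randomized patient who has not withdrawn from data collection. Apply item 7's face-to-face physician or advanced-practice-provider definition, with the same procedure in both arms and staff blinded to arm.
- Keep the two-monthly interview as the source for encounters elsewhere, with a stated look-back period that covers a missed interview.
- State how discrepancies are resolved, and report agreement between interview and records for in-house encounters by arm.
- Reconcile D3 3.c, E2, E3 3.e and E4 item 7 so that they name the same sources for this outcome.

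Patients who withdraw fully remain censored under D2 2.i; the change does not restore their data.

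The cost is SAP and protocol wording plus modest work to map records to the definition. Billing lines include items, such as laboratory assessments, that are not encounters, so written mapping rules and some case review will be needed. The extract is already planned, and patients carry no added burden.

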- Determine the incidence, severity and etiologies of med errors and adverse drug events in kidney transplant recipients and compare these between the intervention and control cohorts.

C2 Secondary Aims

- Measure the total resources utilized (hospital, outpatient, staff effort) to provide care and compare these between the intervention and control cohorts.
- Measure the impact of med errors and adverse drug events on clinical outcomes, including acute rejections, infections, graft loss and death (exploratory aim)

D Study Design

D1 Overview or Design Summary

TRANSAFE Rx is a 12-month, parallel two-arm, 1:1 randomized controlled clinical trial, involving 136 participants (68 in each arm) and measuring the clinical and economic effectiveness of a pharmacist-led intervention, which utilizes an innovative mHealth application to improve medication safety and health outcomes, as compared to usual post-transplant care. The planned study design and interventions of this project were developed from the aforementioned foundational studies. These preliminary studies provided insight into interventions that were clinically effective, efficiently implementable, had a high-rate of patient acceptability and were capable of being scalable to a wide-array of patient populations. It is within this framework that the investigators have designed the TRANSAFE Rx study.

D2 Subject Selection and Withdrawal

2.a Inclusion Criteria

- 1) Kidney transplant recipient between 6 and 36 months post-transplant
- 2) At least 18 years of age
- 3) Transplant MD agrees that patient is eligible to participate

2.b Exclusion Criteria

- 1) Multi-organ recipient
- 2) Patient is incapable of:
 - a. Measuring their own blood pressure
 - b. Measuring their own glucose (if subject has diabetes)
 - c. Self-administering medications
 - d. Speaking, hearing and reading English
 - e. Utilizing the mHealth application, after training

2.c Ethical Considerations

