There is one group formed specifically for the conduct of this study, which is the DSMC. The DSMC will consist of the PI, co-investigators, study coordinator, statistician, data manager and consultants on the proposal. The functions of the DSMC will include: 1) providing scientific oversight; 2) reviewing all serious adverse events (adverse drug events, graft loss and death events, compared across intervention groups) or complications related to the study; 3) monitoring site adherence to the intervention; 4) reviewing summary reports relating to compliance with research protocol requirements; and 5) providing advice on resource allocation. The DSMC will meet according to the safety monitoring plan (Section 4.b.iv) and as necessary by telephone or in person. The recommendations of the DSMC will be reviewed and the PI will take appropriate corrective actions as needed. The intervention clinical pharmacists group will include the clinical pharmacists that were assigned to the intervention arm of the study. During the study, this group will have monthly meetings to discuss the intervention, identify and resolve study related issues and discuss pertinent study-related materials.

H4 Subject Stipends or Payments

Patients will be paid \$50 for each study visit, not including the baseline visit, which will occur during a usual care visit. Thus, if patients complete the 12-month study, they will be remunerated \$100 total, which is provided to cover travel and parking costs associated with the study visits.

H5 Study Timetable

The target dates for major milestones are detailed below. We expect to complete this trial and present final results within 36 months, based on the following:

- IRB submission: Target of July 31, 2017
- IRB approval: Target of August 31, 2017
- Technology development and testing complete: Target of September 30, 2017
- Study Open for Recruitment: Target of October 15, 2017
- Expected Enrollment by June 30, 2018: Target of 68 patients enrolled
- Last Patient Enrolled: Target of March 31, 2019
- Expected Enrollment by June 30, 2019: Target of all 136 patients enrolled, with 68 completed the study
- Last Patient, Last Visit: Target of March 31, 2020
- Complete Data Analysis: Target of April 30, 2020
- Begin to Make Technology Available to Other Pharmacists Managing Non-Transplant Patients: Target of Spring 2020
- Present Final Results at National Meeting (American Transplant Congress, ACCP): Target of May and June 2020

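### The cost analysis is labelled societal, but the costs it plans to count are health-care and intervention costs only

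*Combined protocol and SAP*

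**What the plan says.** Section E4 item 8 (Costs) declares the perspective: "This will be a costs - consequences analysis (CCA) using cost effectiveness methodology, taken from the societal perspective". The same item sets the source and scope of the costs:

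- Source: "Costs associated with care will be assessed based on data from hospital accounting at the study institution, once the study is completed".
- Care counted: inpatient and outpatient care, specified as "hospitalizations, ambulatory care visits, ambulatory procedure visits, acute care/emergency room visits and laboratory assessments".
- Costs specific to the intervention arm: "the costs of the devices and data plan provided to the patients, time necessary for training patients on use of the technology", together with research pharmacist time.
- Care elsewhere: "Costs associated with healthcare encounters that occur outside the study institution will be estimated by acquiring information from the patient", then valued with the study institution's cost/charge ratios.

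Section C2 gives the matching secondary aim: "Measure the total resources utilized (hospital, outpatient, staff effort) to provide care". Section E4 item 7 restricts encounters to face-to-face contacts with a physician or advanced practice provider in a licensed facility. Patient travel is mentioned as a cost only in section H4, as the purpose of the study-visit payment: "which is provided to cover travel and parking costs associated with the study visits".

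**The concern.** A societal perspective counts costs whoever bears them, including patients, families and employers. The listed costs fall on the health-care system or on delivery of the intervention. A report that followed the plan would therefore claim a breadth that its data do not have.

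The missing items are ones the intervention is likely to change. Under section D3, intervention patients log each dose, take home blood pressure and (where applicable) glucose readings, answer side-effect surveys, and have scheduled televisits (twice monthly at high risk) plus triggered ones. The pharmacist's side of this work is costed; the patient's side is not, except perhaps during training. In the other direction, Hypothesis 2 in section A2 expects fewer clinic visits, emergency visits and hospitalizations, which would save patients travel and time.

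Hypothesis 2 also includes reduced costs, and section B2 says that cost-effectiveness of such programmes has yet to be shown adequately. The label is therefore likely to carry into the trial's economic claim.

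**Working it through.** **Label against scope.** The table sets the components of a societal cost beside the plan.

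| Component | Where planned |
|---|---|
| Hospital, clinic, procedure, emergency and laboratory care | E4 item 8 |
| Care at other institutions | E4 items 7 and 8 |
| Devices, data plan, training time, research pharmacist time | E4 item 8 |
| Patient time in self-monitoring, televisits and visits | Not found (training time at most) |
| Caregiver time | Not found |
| Travel to care | Not found as a cost input; H4 mentions it only for the stipend |
| Lost work | Not found |
| Out-of-pocket spending | Not found |

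The schedule in section E2 covers medication errors, adverse drug events, health-care encounters and clinical events, with no item for the last five rows. The additional surveys in section E4 cover sociodemographics, health literacy, depression, social support and trust, not costs.

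**The plan's own cost figure.** Section F1 gives means of $7,658 (control) and $5,169 (intervention), σ = $4,530, and more than 80% power. The inputs used are 52 per arm and two-sided α = 0.05; F1 states these for the encounter comparison just before, and they are assumed to carry over.

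- Difference: 7,658 − 5,169 = $2,489, as stated.
- Standard error: 4,530 × √(2/52) = $888.4.
- Power: Φ(2,489/888.4 − 1.96) = Φ(0.84) = 80.0%. A two-sample t-test gives 79.3%.

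The stated power is thus reproduced at its boundary. It concerns the costs that are counted, and relabelling does not change it.

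**Scale of what is left out.** The documents give no patient-side costs, so these figures are illustrations, not estimates.

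- Break-even: 2,489/365 = $6.82 per day. A net uncounted burden of that size in the intervention arm would cancel the planned saving.
- Under an assumed 10 to 30 minutes of patient time per day at $10 to $20 per hour, the yearly burden runs from (10/60) × 10 × 365 ≈ $608 to (30/60) × 20 × 365 = $3,650. The range spans the break-even point. It ignores any travel and time saved by fewer visits.
- Holding σ at $4,530 and 52 per arm, power is Φ((2,489 ∓ x)/888.4 − 1.96), where x is the net omitted cost:

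| x per patient | Falls on the intervention arm | Favours the intervention arm |
|---|---|---|
| $250 | 71% | 87% |
| $500 | 61% | 92% |
| $1,000 | 39% | 98% |

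Nothing in the documents says which column applies, or which row.

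**The case against.** The case for leaving the text alone is reasonable in several respects. Section C2 lists resource use as a secondary aim and states its scope. A cost-consequences analysis shows its components, so a careful reader can see what was counted. The cost comparison as computed would not change. These arguments stand, and they make this a correction of label and conclusion. They do not make the word societal accurate.

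Two other defences are weaker. The training-time item could be read as including patients' time, but it would then cover training only. The phrase about all costs of inpatient and outpatient care is broad but still describes care. One caution does hold: parts of the document, including some of the attachments, were not available for review. The accurate statement is that no available section plans these costs, not that none are collected.

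A reader might also infer three stronger claims that the documents do not support.

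- *That omitted travel is about 12% of cost.* Applying the $50 study-visit payment to every encounter gives 18.4 × 50 = $920 in the control arm, and 920/7,658 = 12.0%. That is a level in one arm. The between-arm difference is 920 − 17.0 × 50 = $70, or 70/2,489 = 2.8% of the planned saving, and it favours the intervention. The $50 is also a flat stipend for two research visits attended by both arms, not a measured travel cost per encounter.
- *That the planned saving is wrong in a known direction.* The added patient tasks and the avoided visits pull opposite ways, and neither is quantified.
- *That the analysis takes a single provider's view.* Encounters at other institutions are costed too, so the scope is wider than one hospital.

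**Conclusion.** The mismatch between the declared perspective and the planned costs is real. As written, the plan supports a conclusion about health-care and intervention costs, not about cost to society. The size and sign of the omitted net cost cannot be derived from the documents. The only anchors are the planned saving of $2,489 ($6.82 per day) and power for cost that sits at about 80%, so a modest omitted cost could matter to a societal claim.

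This rests on two assumptions: that the unavailable pages contain no patient-cost instrument, and that the lists in E4 item 8 are meant to describe the scope of the analysis. Severity is minor. The primary medication-error and adverse-drug-event analyses, the sample size and the computed cost comparison are unaffected.

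**What to change.** In section E4 item 8, replace *societal perspective* with *health-care sector perspective (health-care plus intervention costs)*. Limit the cost conclusion under Hypothesis 2 to that perspective, and name patient and caregiver time, travel, lost work and out-of-pocket spending as not counted. Because the label will define the scope, also say whether outpatient prescription drugs are included; the item does not name them. A scenario valuing each encounter at $50 should not be added, since that figure is a research-visit stipend.

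The change costs one phrase and a sentence or two, with no new data. The downside is a narrower economic claim. Keeping the societal label would instead mean collecting and valuing the patient-side costs in both arms, for example at the existing bimonthly interviews.
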